4.4.1 Specific clinical management of cooling group

This group will be cooled according to the normal protocols of the hospital as this is standard treatment. In standard care, some of the cooled babies will undergo MRI brain assessment around 48 hours of life in addition to the routine MRI brain assessment around 7 days of life, to provide early information about severity of brain injury. In the study, all the babies will undergo MRI brain examination around 48 hours of age. At this time point the babies will be continuing the cooling therapy. Our team is experienced in looking after the cooled babies during transport and MRI examination with least discomfort to the babies. Moreover, all the babies will receive continuous morphine infusion to keep them comfortable during cooling, as part of their standard protocol.

4.4.2 Specific clinical management of Xenon+cooling group

After initial resuscitation and attainment of a stable state, and inclusion in the study, the tracheal tube would be replaced with a cuffed commercially available tracheal tube (Kimberley-Clark microcuff) of the same or 0.5mm smaller size as the existing one and the cuff inflated until leakage of gas around the cuff had ceased audibly and according to the ventilator monitor. This particular tube has a high volume, low pressure cuff and is specifically designed for long term use on the paediatric or neonatal intensive care unit. The cuff pressure will be monitored and recorded at the time of initial inflation, during Xenon administration every 2 hours and just prior to final deflation. If there are any post extubation adverse events such as stridor, or extubation fails secondary to vocal cord, nerve or subglottic damage, these will be recorded. In our

Neonatal Xenon Breathing Device: CoolXenon3 Study	Protocol	CI/2013/4414
	Version	Issue 2, Revision 3
	Issue Date	18 Sept 2019
	Page	25 of 79

recent studies, of the 28 babies given Xenon, one developed post-extubation stridor requiring steroids*.

1. The dose (fraction of Xenon in breathing gas) planned for each patient in the Xenon+cooling group will be 50%. It will be applied for 18 hours. It will be commenced as soon as is practicable but no later than 5h after birth once all the entry criteria / consent requirements have been met.
2. If a baby is being retrieved from another local hospital to the study centre (Bristol) using the existing Bristol-provided retrieval team and ambulance, AND they have been consented and randomised to receive Xenon AND if it is deemed probable that the delay between birth and the start of Xenon in Bristol would exceed an interval of 5 hours, then if logically possible an assigned research team member will accompany or meet the retrieval team and commence Xenon delivery at the local hospital or during the return transfer of the baby to Bristol.
3. Full data sets will be acquired in two groups of 26 patients. The mortality rate in the patients referred for cooling to Bristol is 10.3%.
4. Cooling will be for 72 hours using the clinically chosen cooling device in both groups, as is current standard practice for cooling.
5. In standard care, some of the cooled babies will undergo MRI brain assessment around 48 hours of life in addition to the routine MRI brain assessment around 7 days of life, to provide early information about severity of brain injury. In the study, all babies will undergo MRI brain examination around 48 hours of life. At this time point, babies will have completed the xenon therapy and will continue with cooling therapy. Babies will be kept comfortable with continuous morphine infusion as per the standard local protocol. Our team is experienced in transporting cooled babies to the MRI and looking after the cooled babies during MR examination. This MRI will provide valuable data regarding the severity of brain injury, early effect of xenon on brain injury and determine the progression of brain injury with xenon+cooling compared with cooling alone.

4.5 Further information on the oxygen fraction in the breathing gas mixture

The Xenon we intend to use (LenoXe) is currently licensed for anaesthesia in adults. The LenoXe SmPC specifies that Xenon should be administered (for adult anaesthesia) with at least 30% oxygen in the breathing gas mixture.

It is our intention in this study to administer an oxygen fraction in the breathing gas to ensure adequate oxygenation of the blood of the neonate, but not to give an excess, as there is also a real risk of hyperoxic brain damage in this group of neonates if the oxygen fraction is too high. Consequently, in a neonate with normal lungs being sedated and ventilated for cooling rather than for any lung problems, the inspired oxygen fraction could be lower than 30% (air is 21% for example). The lowest fraction of oxygen in the breathing gas will always be used, sufficient to maintain an oxygen saturation on blood gas analysis or pulse oximetry of at least 96%, especially as hyperoxia is considered to be very harmful to the brain in infants who have just had a hypoxic-ischaemic insult.

The reason the LenoXe SmPc specifies 30% oxygen is following the normal practice of anaesthesia using other gases and vapours, because during anaesthesia in adults the ventilation/perfusion mismatch in the lungs becomes very slightly less efficient than in the awake state. This is due to changes in muscle tone, diaphragm position/shape and effects of gravity on distribution of blood flow through regions of the lung. Although humans are designed to breathe air (21% oxygen), a patient with normal lungs under anaesthesia would traditionally be given approximately 30% oxygen (more if there were any lung problems as clinically indicated).

It should be noted that this anaesthetic tradition to use a slightly higher inspired oxygen fraction than might strictly be required developed before it became commonplace and later mandatory to use pulse oximetry to continuously monitor oxygen saturation of the blood and end-expired carbon dioxide monitoring to continuously monitor the adequacy of ventilation (in terms of carbon dioxide removal from the blood) which became widespread in the late 1980's / early 1990's.

In the neonates of this study the situation is different as they have all recently suffered a hypoxic-ischaemic (HI) insult to the brain and other organs around birth. Ventilating them with a gas mixture containing an oxygen fraction even slightly higher than necessary is considered highly undesirable as in this situation it can actually worsen the subsequent brain

* In a recent very large study of cuffed tracheal tubes for anaesthesia in infants and neonates, the use of a cuffed tube did not increase risk of post-extubation stridor. In 2246 children, post-extubation stridor was noted in 4.4% of those with a cuffed tracheal tube and 4.7% of those with uncuffed tubes, with a much lower tube exchange rate in the cuffed tube group.

Neonatal Xenon Breathing Device: CoolXenon3 Study	Protocol	CI/2013/4414
	Version	Issue 2, Revision 3
	Issue Date	18 Sept 2019
	Page	26 of 79

injury. This explains recent changes to resuscitation equipment for the newborn where the 100% oxygen supplies have been replaced with air/oxygen blenders. The new ILCOR Resuscitation Guidelines³⁹ state that term newborns should first be resuscitated in air, then with a higher concentration of oxygen if pulse oximetry or clinical signs suggest poor oxygenation.

It is worth noting that variations in ventilation/perfusion throughout the regions of a healthy neonatal lung are less affected by anaesthesia/sedation than in a (much larger) adult so the physiological (anaesthetic) justification for automatically using 30% oxygen is weaker in the neonate.

However the more relevant points with respect to this study are that although in anaesthesia practice it may be normal and quite harmless to set an inspired oxygen fraction slightly higher than strictly necessary, in neonates that have suffered a hypoxic-ischaemic insult to the brain and other organs around birth, it is considered **highly undesirable** to administer an inspired oxygen fraction that is any higher than the amount required for adequate oxygen delivery to the organs. We have recently shown experimentally that 30 min of 100% oxygen after hypoxia-ischaemia increased injury⁴⁰. Consequently,

- we monitor *oxygen saturation of the blood* of the neonate using continuous pulse oximetry (with audible and visual alarms),
- we continuously monitor *adequacy of ventilation* with a neonatal end-expired carbon dioxide monitor which reflects the systemic arterial carbon dioxide content. While mandatory in adult intensive care practice this is not yet the case in neonatal practice due to unavailability of suitable monitors for neonates, a situation which is now changing.
- We also routinely monitor oxygen saturation of the blood periodically in ventilated neonates by analysing arterial blood samples using a blood gas analyser. In neonates that have experienced an HI insult around birth the attending physicians are not only checking that the oxygen content is not too low but also *they are checking it is not too high*. A slight elevation that would normally be acceptable is not acceptable in this particular group of babies and if too high they will actively request that the inspired oxygen fraction in the breathing gas be reduced.
- As a result of the above, *the inspired breathing gas might contain a theoretical maximum oxygen fraction of 40% as stated in the protocol if clinically required due to lung problems, but also this may for the above reasons be deliberately set as low as is required to maintain an oxygen saturation of >=96% if the lungs are normal.*

The desired inspired Xenon fraction is to be set at 50% as per the protocol. The “balance gas” in situations where a moderate oxygen fraction is being used will be nitrogen. This will simply be room air which although containing 21% oxygen is otherwise mainly composed of nitrogen.

At the end of the prescribed period of Xe delivery the tracheal tube would be reconnected directly to the mechanical ventilator and normal ventilation and gas mixtures set as clinically appropriate. The cuff of the tracheal tube would be deflated. This tracheal tube would be replaced with an uncuffed tube at a later timepoint as clinically indicated or kept until the patient was extubated after rewarming. Cooling regimes last for 72hrs before slow rewarming commences (0.1-0.4°C per hour). The standard cooling protocol would continue for many more hours after cessation of the additional Xenon regime.

4.7 Risks/benefits and risk minimisation

4.7.1 Potential risks from Xenon

The known effects of Xenon in humans have all been derived from adult anaesthesia studies. Xenon is known to have minimal effects on the strength of the heart contractions or the blood pressure⁴¹⁻⁴⁴. A slight slowing of pulse rate has been seen in some studies but this is often not statistically significant.

Xenon is analgesic and causes sedation. These might be considered useful properties in a sedated baby on an Intensive Care Unit.

Xenon is a dense gas. Erring on the side of caution we would not use it in this early study in any baby with airway narrowing or similar lung problems, the exclusion criteria reflect this. Note that the use in piglets weighing 1.5 kg and small airways did not display any ventilation/airway problems (Appendix 4). As with other anaesthetic gases it can diffuse into gas filled cavities in the body such as the bowel. This happens only slowly in adults, and more slowly than with other anaesthetic gases such as nitrous oxide, however for this reason it would not be used in any situation where the bowel was obstructed (our Xenon inclusion criteria reflect this).

In animal neonatal studies, there have been no side effects and we can document:

- Improved neuroprotection¹⁸
- Better cardiovascular stability³⁴
- No extubation delay (delay coming off the mechanical ventilator)¹⁸
- No increase in oxygen requirements¹⁸

From studies using Xenon as an anaesthetic in adults, of which there are many, the experience is that Xenon has remarkably few side effects and in particular produces minimal haemodynamic disturbance compared to conventional anaesthetics⁴¹⁻⁴⁴.

As Xenon is almost chemically inert, it is eliminated from the body completely unchanged – it is eliminated from body tissues via the circulation and lungs at the end of the procedure. Xenon, although uncommonly used due to its high cost, does therefore have a license for use as an anaesthetic in adults in several countries, including the UK.

In 2010/2011 our group undertook and successfully completed the first human neonatal feasibility/safety study of Xenon+cooling, mainly 50% Xenon for periods of up to 18hrs. All survivors underwent a Bayley examination at 18 months of age. From this study, in terms of safety, we can document:

- It is feasible to give 50% Xenon for up to 18h in infants undergoing therapeutic hypothermia¹⁰

Neonatal Xenon Breathing Device: CoolXenon3 Study	Protocol	CI/2013/4414
	Version	Issue 2, Revision 3
	Issue Date	18 Sept 2019
	Page	28 of 79

- Only 0.2-0.3L/hour Xenon was used with a closed loop Xenon breathing system
- A cuffed tube did not adversely affect ease of extubation
- Xenon is sedative and other sedation is needed when Xenon is discontinued
- No significant cardiovascular or respiratory changes before, during and after Xenon
- In one child with abnormal/immature lungs, Xenon did not increase FiO₂ requirement.

See Appendix 3

From the perspective of babies who may already be unwell, the main points to note therefore are:

- i) Xenon is not broken down to any “by products” by the metabolism of the body as many other drugs are, as it is an almost chemically “inert” elemental gas.
- ii) Xenon is very free of side-effects in the adult experience, which may be due to this “inert” nature, but perhaps most importantly:
 - Xenon is eliminated from the body completely unchanged via the lungs within a few breaths. This means that if there is any problem, unlike the situation with any drug injected into a vein, Xenon is a *reversible treatment*, ie, it can be easily removed completely, rapidly and unchanged from the body at any time. *This ability to reverse application of Xenon and rapidly eliminate it unchanged from the patient in the event of any problem is, although unusual, a key factor from the perspective of safety.* When the Xenon is being administered, a special breathing circuit will be connected to the ventilator designed for this purpose. It will be operated by a member of the team who has documented experience running and troubleshooting with this equipment.

4.7.2 Potential risks from breathing system

We are using the same breathing circuit to deliver this gas as in previous MHRA approved studies; CoolXenon and CoolXenon2 (MHRA study references CI/2009/0043, CI/2011/0061 respectively). This has been developed over many years by a Consultant Anaesthetist who is a co-researcher on this team and world leader on this subject. Prior to use in these human studies, it has been tested extensively in laboratory neonatal pig simulations of the condition (see section 4.3.1).

To minimise risk of any technical problems:

- a. The equipment meets all necessary international medical device safety and quality standards. It has been professionally constructed using medical grade materials.
- b. The design is such that the Xenon system is placed between the standard mechanical ventilator and the baby. This means that if there is any technical problem, the ventilator can be immediately connected directly to the baby and the Xenon system removed in one simple intuitive operation.
- c. The gas composition, in particular oxygen, of the circuit gas will be continuously measured, as will Xenon and the ETCO₂ (which reflects the arterial value).
- d. The breathing system has an overpressure release valve in the event of any mishap.
- e. Furthermore, if there were any problem due to the Xenon gas itself, reconnection directly to the ventilator would also allow all the Xenon to be breathed out from the baby within a few breaths, i.e. the Xenon treatment is rapidly reversible.
- f. The Xenon will be delivered by trained personnel who have also been involved with laboratory trials using Xenon in animal models and previous MHRA approved clinical trials involving the device.
- g. The possibility of interaction between the Xenon gas and the materials of the breathing circuit has been considered. As Xenon is chemically “inert” i.e. does not form chemical compounds except in the most extreme circumstances, there is no perceived risk.
- h. A full risk assessment in accordance with standard medical device regulatory requirements has been undertaken and thoroughly documented.
- i. The device meets all of the Essential Requirement of the EU Medical Device Directives, with the exception of those being evaluated in the study.

This design of breathing system has now been evaluated in two MHRA approved studies with this patient population. Summary data from the CoolXenon2 study:

Neonatal Xenon Breathing Device: CoolXenon3 Study	Protocol	CI/2013/4414
	Version	Issue 2, Revision 3
	Issue Date	18 Sept 2019
	Page	29 of 79

	Cooling only (n=14)	Cooling + Xenon (n=14)
Birth weight, gram	3648 ± 503	3455 ± 394
Gestational age, weeks	40.7 ± 1.3	40.1 ± 1.3
Female, nr (%)	8 (57)	8 (57)
Outborn, nr (%)	9 (64)	8 (57)
Apgar 1 minute	2 (0-2.25)	1 (1-3.25)
Apgar 5 minutes	4 (3-5.25)	4 (2.5-6)
Apgar 10 minutes	6 (3.75-7)	5 (3-8.25)
Cord pH	7.03 ± 0.17	7.00 ± 0.19
Cord BE	-12.9 ± 5.2	-12.3 ± 8.7
Received anticonvulsants,	8 of 14	9 of 14
Received inotropes, %	71	57

Table 1: Summary preliminary data from CoolXenon2 study (BW, GA, Cord pH and BE are mean±SD apart, Apgar is median with IQR)

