4.0 Study Design

This is a prospective randomised comparative clinical outcome study conducted in St Michael's Hospital, Bristol and Hammersmith Hospital, London.

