4.3 Randomisation

The babies entered into the study will be randomised into two groups on a 1:1 basis. Randomisation will be via sealed opaque envelopes containing details of treatment allocation and [an] identifying adhesive label(s) to be attached to the CRF binder. Neonates meeting all the entry criteria can be included. In this study early randomisation before 5h of age is paramount. The maximum target delay before starting cooling is before 3h of age and for Xenon this value is 5h of age. These are maximum delay values however, so consent and randomisation need to take place as early as possible.

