5.3.2 Proof-of-Concept and Pilot Clinical Studies

Neonatal Xenon Breathing Device: CoolXenon3 Study	Protocol	CI/2013/4414
	Version	Issue 2, Revision 3
	Issue Date	18 Sept 2019
	Page	36 of 79

The Bristol group has undertaken two studies involving the use of inhaled Xenon. A clinical feasibility/safety study in 14 human neonates of inhaled Xenon in combination with cooling using this equipment design to deliver Xenon was successfully completed in March 2011. A further study has recruited 28 infants. In the CoolXenon1 or CoolXenon2 studies there were no significant physiological or biochemical changes or other problems attributable to the Xenon gas or the use of the NXBD.

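### For some retrieved infants, whether Xenon can start in time is settled only after allocation, so a Xenon-arm infant can go untreated; a check before randomisation would close the gap cheaply

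*Protocol*

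**What the plan says.** **Outreach for retrieved infants.** Section 4.4.2 item 2 covers infants being brought to Bristol by the retrieval team. It applies when "AND they have been consented and randomised to receive Xenon AND if it is deemed probable" that starting Xenon in Bristol would overrun 5 h from birth. In that case, "then if logically possible an assigned research team member will accompany or meet the retrieval team" and begin Xenon locally or in transit. The Overview (1.0) describes the same outreach for a retrieved infant without the proviso about logistics.

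**Entry and randomisation.** Section 4.3 says "Neonates meeting all the entry criteria can be included". It calls for randomisation before 5 h of age, which is also the limit for starting Xenon. The Xenon entry lists in 4.1.3 and 6.2.2 contain the infant's condition and current age. Neither asks whether a device and operator can reach the infant in time. The Overview, however, words starting Xenon within 5 h as part of being accepted into the study.

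**Who runs the device.** Section 4.7.1 says "It will be operated by a member of the team who has documented experience running and troubleshooting with this equipment". Section 4.7.2 item (f) says "The Xenon will be delivered by trained personnel who have also been involved with laboratory trials using Xenon in animal models". The same item adds a second kind of background, namely involvement in "previous MHRA approved clinical trials involving the device". The trial is "conducted in St Michael's Hospital, Bristol and Hammersmith Hospital, London", while section 5.3.2 says "The Bristol group has undertaken two studies involving the use of inhaled Xenon".

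**The concern.** Under 4.4.2 item 2, whether outreach can be provided is worked out once the infant is known to be in the Xenon arm. If it cannot, the infant is already randomised and may receive cooling alone. Nothing equivalent can happen to a control infant, because control treatment needs no device and no visiting operator.

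Either way of handling such an infant has a price. Kept in the Xenon arm, the infant pulls the expected Bayley difference towards zero. Left out, the infant is removed from one arm only, on a post-randomisation event linked to distance and delay. The choice of analysis set may well be made in a statistical analysis plan that was not available here, and its absence from the protocol is no criticism. Neither choice undoes the problem, whereas a check before allocation prevents it.

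**Working it through.** **1. The sequence as written.**

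| Step | Section | Is an achievable Xenon start checked? |
|---|---|---|
| Acceptance | 1.0 | Yes, in wording: starting Xenon within 5 h is part of acceptance |
| Entry lists | 4.1.3, 6.2.2 | No: current age only |
| Randomisation | 4.3 | No: permitted up to the Xenon start limit itself |
| Outreach | 4.4.2 item 2 | After allocation to Xenon, and conditional |
| Outreach | 1.0 | Stated without that condition |

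Section 8.5.3 also places reintubation with a cuffed tube, an X-ray and a blood gas before Xenon. An infant randomised close to 5 h can therefore satisfy every listed criterion and still have no on-time start available.

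**2. Who is affected.** Only retrieved infants expected to overrun 5 h on reaching Bristol. Infants born outside the study hospital are put at 61% in 4.2 and at more than 90% in 1.0, 6.0 and 8.1. The share of these who would overrun is not given.

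**3. Size.** The protocol gives no rate of randomised but untreated infants, so there is no figure to reproduce. Let k of the 26 Xenon infants go untreated (26 per group, section 4.10). Assume analysis as randomised, no Xenon effect in untreated infants and the same effect in all treated ones. Then:

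share of the full difference retained = 1 − k/26

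| k (assumed) | Calculation | Retained |
|---|---|---|
| 0 | 1 − 0/26 | 100% |
| 1 | 1 − 1/26 | 96.2% |
| 2 | 1 − 2/26 | 92.3% |
| 5 | 1 − 5/26 | 80.8% |

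I do not convert this into lost power. Section 10.1 plans descriptive statistics with estimated differences, and 2.3 says there was no validated early predictor on which to base a power calculation, so there is no planned power to fall short of.

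**4. What the earlier experience shows.** Section 2.3 reports about 40% of potential recruits lost to the time limit before Xenon was run in the ambulance, and none missed afterwards. Both figures concern recruitment, not randomised infants left untreated, so 40% must not be used as k/26. The extension was planned for 8 infants, 4 per group. Taking those as the denominator (an assumption), the exact one-sided 95% upper bound for zero events in n is 1 − 0.05^(1/n):

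- n = 8: 1 − 0.05^(1/8) = 31%
- n = 4: 1 − 0.05^(1/4) = 53%

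The record is favourable but too small to exclude a material rate. It does not show that infants went untreated.

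**5. Operator descriptions.** Section 4.7.2(f) is narrower than 4.7.1, but the two are compatible, since one person can meet both. Neither is mentioned in 4.4.2 item 2, which speaks only of an assigned research team member.

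**The case against.** The strongest reply is that the timing problem has been solved. The delivery system is mounted in the ambulance (1.0), and no recruit has been missed on time since (2.3). Section 8.3 has local hospitals typically calling within 1 h of age to discuss eligibility, transport and possible inclusion. Section 2.3 counts earlier late infants as lost recruits, which suggests they were screened out before allocation. This has weight: practice may already be what the fix asks for. It does not change the order written in 4.4.2 item 2, or the absence of the check from the entry lists, and the supporting record is small and comes from Bristol.

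A reader might infer three stronger points that the documents do not support:

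- **That the effect is diluted.** No untreated rate is given, and dilution also depends on the analysis set.
- **That operator qualification decides whether outreach is possible.** The text ties the proviso to logistics and does not mention the experience described in 4.7.2(f).
- **That London must choose between untreated infants and breaching 4.7.2(f).** Section 5.3.2 attributes the earlier studies to Bristol, but no text available for this review says who runs the device in London or what experience they have. The schematic and study administration pages, where this might appear, were not in the copy reviewed.

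**Conclusion.** The point holds in a limited form. For retrieved infants likely to pass 5 h, the protocol puts a conditional feasibility step after allocation, contradicts it with an unconditional statement in the Overview, and has no entry criterion that would catch the problem first. A Xenon-arm infant can therefore go untreated, leading to either dilution or one-sided exclusion.

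Each such infant is 3.8% of the arm. Under the assumptions above, one to five of them would leave 96% to 81% of the expected Bayley difference. The true number is unknown and may be zero. This is a cheap improvement, not a defect shown to have biased the trial. The difference between the two operator descriptions is a secondary matter of wording and does not itself cause dilution.

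**What to change.** - In 4.1.3, 6.2.2 and 4.3, require confirmation before the envelope is opened that a device and an operator can reach the infant within the protocol's existing Xenon start limit. Apply this to every infant, whatever the later allocation, so that it acts equally on both arms. It carries the acceptance wording of the Overview into the operative criteria.
- Move the logistics proviso in 4.4.2 item 2 to that step, and reconcile the item with the Overview.
- As a minor edit, reconcile the operator descriptions in 4.7.1 and 4.7.2(f) and say how they apply at the London site. The content of the standard is for the sponsor to decide.

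The cost is protocol wording and one eligibility tick-box. The downside is that a few infants who cannot be reached in time are not enrolled.
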